4.1 Dose modification, interruption or discontinuation of treatment

If an adverse event is clearly associated to one of study drugs, the dose adjustment directed for that study drug will be followed; however, if the causality is not clear, then it may be necessary to adjust both study drugs. Dosing adjustments will be discussed with the sponsor. If a patient experiences a DLT then treatment with Sonidegib plus buparlisib must be stopped and the patient may be discontinued from the study. However, following resolution of the DLT to CTCAE Grade 1 or to the patient's baseline value, the patient may continue to receive study treatment with a 50% dose reduction for either sonidegib, buparlisib or both, if appropriate, at the discretion of the investigator and after discussion with the Sponsor.

If a patient requires a dose delay of > 21 days due to an sonidegib- or buparlisibrelated toxicity, then the patient must be discontinued from the study; however, if the patient is obtaining clinical benefit (ie, SD, PR, or CR), the patient may continue treatment at the same or at a reduced dose following discussion between the investigator and Novartis. All patients will be followed for AEs and SAEs for 30 days following the last dose of sonidegib and/or buparlisib. If the administration of study treatment was interrupted for reasons other than toxicity, then treatment with Sonidegib and buparlisib may be resumed at the same dose.

Patients who experience hematologic, renal, hepatic, or muscle toxicities should receive follow up and dosing modifications for sonidegib as per Table 9 and 10 below. Specific instructions for follow-up and dosing modifications for sonidegib are described in detail in Table 9. Patients who experience muscle toxicity, regardless of whether the toxicity meets the criteria described for a DLT, should be receive follow-up and dosing modifications specified in Table 9 below.

Table 9. Recommended dose modifications and dose delays for suspected sonidegib** treatment-related toxicities	
Worst toxicity CTCAE grade* (value)	During a cycle of therapy
Не	ematologic
Neutropenia (ANC)	
Worst toxicity CTCAE grade* (value)	During a cycle of therapy
Grade 1 (ANC < LLN - 1500/mm ³)	Maintain dose level
Grade 2 (ANC < 1500 - 1000/mm ³)	Maintain dose level

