Grade 4 Total bilirubin > 10.0 x ULN	Discontinue study drug. Consider if hospitalization is appropriate.

Table 9. Recommended dose modifications and dose delays for suspected sonidegib** treatment-related toxicities	
Worst toxicity CTCAE grade*(value)	During a cycle of therapy
	AST or ALT
Grade 1 (> ULN - 3.0 x ULN)	Maintain dose level
Grade 2 (> 3.0 - 5.0 x ULN)	Maintain dose level
Grade 3 (> 5.0 - 20.0 x ULN)	Omit dose until resolved to ≤ Grade 1 or baseline then: •• If resolved in ≤ 7 days, then maintain dose level •• If resolved in > 7 days, then implement 50% dose reduction
Grade 4 (> 20.0 x ULN)	Omit dose until resolved to ≤ Grade 1 or baseline, then implement 50% dose reduction. Consider if hospitalization is appropriate
	Cardiac
Cardiac - prolonged QTc interval Grade 3 (QTcF > 500 msec or >60 ms from baseline on at least 2 separate ECGs taken within 1 hour)	First Occurrence: ◆ Omit dose ◆ Perform an analysis of serum potassium and magnesium, and if below lower limit of normal, correct with supplements to within normal limits. Concomitant medication usage must be reviewed. ◆ Perform a repeat ECG within one hour of the first QTcF of > 500 ms ◆ If QTcF remains > 500 ms, repeat ECG as clinically indicated but at least once a day until the QTcF returns to < 480 ms. ◆ Once QTcF prolongation has resolved, study treatment may be restarted with a 50% dose reduction Second Occurrence: ◆ discontinue patient from study drug

Cardiac - prolonged QTc interval	Discontinue patient from study drug
Grade 4	

Table 9. Recommended dose modifications and dose delays for suspected sonidegib** treatment-related toxicities	
Worst toxicity CTCAE grade* (value)	During a cycle of therapy
Otl	her Cardiac Events
Grade 1	Maintain dose level
Grade 2	Implement 50% dose reduction of buparlisib
Grade 3	Omit dose and discontinue study drug
Grade 4	Omit dose and discontinue study drug. Consider if hospitalization if appropriate
Oth	er adverse events**
Grade 1	Maintain dose level
Grade 2	Implement 50% dose reduction
Grade 3	Omit dose and discontinue study drug
Grade 4	Omit dose and discontinue study drug

Grade 3	Omit dose and discontinue study drug
Grade 4	Omit dose and discontinue study drug
	Consider if hospitalization if appropriate
111 1 110 1 1 1 1 1	i di

All dose modifications should be based on the worst preceding toxicity.

If the dose-limiting toxicity recurs in a patient following dose reduction, then further therapy with sonidegib will not be continued.

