If a patient requires a dose interruption of > 21 days from the intended day of the next scheduled dose because of a sonidegib-related toxicity, then the patient must be discontinued from the study.

*Common Toxicity Criteria for Adverse Events (CTCAE Version 4.0).

** If the investigator deems that a recommended dose reduction or the recommendation to maintain the same dose level is not in the best interest of the patient, this decision may be discussed with Novartis on a case-by-case basis.

Criteria for follow-up and dosing modifications for buparlisib are described in detail in Table 10.

For overlapping toxicities of sonidegib and buparlisib, specifically hematologic, renal and hepatic toxicities, BOTH sonidegib and buparlisib will be reduced or discontinued depending on toxicity grade per the guidelines listed below for each drug (Tables 9 and 10).

Table 10. Recommended dose modifications and dose delays for suspected buparlisib treatment-related toxicities		
Worst toxicity CTCAE grade* (value)	During a cycle of therapy	
	Hematologic	
]	Neutropenia (ANC)	
Grade 1 (ANC < LLN - 1500/mm ³)	Maintain dose level	
Grade 2 (ANC < 1500 - 1000/mm ³)	Maintain dose level	
Grade 3 or 4 (ANC < 1000 - 500/ mm ³ or < 500/mm ³)	 Omit dose until resolved to ≤ Grade 1, then: If resolved in ≤ 7 days, implement 50% dose reduction If resolved >7 days, discontinue drug If a Grade 4 event, consider hospitalization if appropriate 	
Thrombocytopena		
Grade 1 (PLT < LLN - 75 x 10 ⁹ /L)	Maintain dose level	
Grade 2 (PLT < 75 - 50 x 10 ⁹ /L)	Maintain dose level	

Grade 3 (PLT $< 50-25 \times 10^9/L$)	Omit dose until resolved to ≤ Grade 1, then:	
	 If resolved in ≤ 7 days, then maintain dose level If resolved in > 7 days, then implement 50% dose reduction 	
Grade 4 (PLT < 25 x 109/L)	Omit dose until resolved to ≤ Grade 1, then implement 50% dose reduction. Consider if hospitalization is appropriate	
	Renal	
	Serum creatinine	
Serum creatinine <1.5 x ULN	Maintain dose level	
Serum creatinine 1.5-3 x ULN	Omit dose until resolved to ≤ Grade 1, then: •• If resolved in ≤ 7 days, then maintain dose level •• If resolved in > 7 days, then implement 50% dose reduction (consider checking serum CK, if not already done)	
Table 10. Recommended dose modifications and dose delays for suspected buparlisib treatment-related toxicities		
Worst toxicity CTCAE grade* (value)	During a cycle of therapy	

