Grade 4	Discontinue buparlisib. Consider if hospitalization is appropriate According to the investigators discretion, a paired skin biopsy could be obtained (from both an affected and an unaffected skin area for local histopathology assessment) if clinical appropriate.
Table 10. Recommended dose modifications and dose delays for suspected buparlisib** treatment-related toxicities	
Worst toxicity CTCAE grade* (value)	During a cycle of therapy
Fatigue (asthenia)	

Grade 1 Fatigue relieved by rest	Maintain dose level
Grade 2	Reduce study drug dose by 50% of prior
Fatigue not relieved by rest; limiting instrumental ADL	

Grade 3	Discontinue study drug
Fatigue not relieved by rest; limiting	
self care ADL	
Grade 4	Discontinue buparlisib.
	Consider if hospitalization is appropriate
	Pneumonitis
Please see Section 4.1.2.3.2; Table 14; 6.2.6.1.1.	and/or buparlisib Investigator Brochure Section
0	ther adverse events
Grade 1	Maintain dose level
Grade 2	Implement 50% dose reduction
Grade 3	Omit dose and discontinue study drug
Grade 4	Omit dose and discontinue
	study drug Consider if
	hospitalization if appropriate
	Other notes:
Table 10 Pesammen	
	ded dose modifications and dose delays buparlisib treatment-related toxicities
Worst toxicity CTCAE grade* (value)	During a cycle of therapy
Note: Omit dose for ≥ Grade 3 vomiting or Grade 3 nausea only if the vomiting or nausea cannot be controlled with optimal antiemetic	
All dose modifications should be based on the worst preceding toxicity.	
If the dose-limiting toxicity recurs in a patient following dose reduction, then further therapy with sonidegib will not be continued.	
If a patient requires a dose interruption of > 21 days from the intended day of the next scheduled dose because of a sonidegib-related toxicity, then the patient must be discontinued from the study.	
** Common Terminology Criteria for A	Adverse Events (CTCAE) version 4.03.

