4.1.1 Monitoring of buparlisib suspected toxicities

Patients whose treatment is interrupted or permanently discontinued due to an adverse event or clinically significant laboratory value, must be followed at least once a week for 4 weeks, and subsequently at 4-week intervals, until resolution or stabilization of the event, whichever comes first. If a patient requires a dose delay of > 21 days from the intended day of the next scheduled dose, then the patient should be discontinued from the study. If the patient requires more than 1 dose reductions, the patient should be discontinued from the study (ie, patients cannot be treated below a 50% dose reduction). All patients must be followed for adverse events and serious adverse events for 28 days following the last dose of buparlisib. All SAEs must be reported to Novartis as detailed in Section 4.3.4.2.

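### Two dosing lines name the wrong drug for their table: the Table 10 (buparlisib) recurrent-DLT footnote stops only sonidegib, and the Table 9 (sonidegib) Grade 2 other-cardiac row reduces only buparlisib

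*Combined protocol and SAP*

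**What the plan says.** Section 4.1 assigns Table 9 to suspected sonidegib toxicities and Table 10 to suspected buparlisib toxicities. For an event clearly associated with one drug, "the dose adjustment directed for that study drug will be followed"; if causality is not clear, both drugs may need adjusting. Section 5.1 adds that study drug means the combination and that a single drug is named when it alone is meant.

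The two lines at issue:

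- **Table 10 footnotes.** On recurrence: "If the dose-limiting toxicity recurs in a patient following dose reduction, then further therapy with sonidegib will not be continued". The same sentence stands under Table 9. The next Table 10 footnote, on interruptions over 21 days, also refers to toxicity related to sonidegib.
- **Table 9, Other Cardiac Events, Grade 2.** "Implement 50% dose reduction of buparlisib". The same words stand in the matching Table 10 row.

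The surrounding rules in Sections 4.1 and 4.1.1:

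- "If a patient experiences a DLT then treatment with Sonidegib plus buparlisib must be stopped"; after resolution, "the patient may continue to receive study treatment with a 50% dose reduction for either sonidegib, buparlisib or both", at the investigator's discretion and after discussion with the sponsor.
- "If the patient requires more than 1 dose reductions, the patient should be discontinued from the study" (Section 4.1.1, on buparlisib toxicities).
- For overlapping hematologic, renal and hepatic toxicities, "BOTH sonidegib and buparlisib will be reduced or discontinued depending on toxicity grade", following each drug's table.
- Where the investigator thinks a recommended action in Table 9 is not in the patient's interest, "this decision may be discussed with Novartis on a case-by-case basis".

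**The concern.** Each line sits in one drug's table and directs action at the other drug. Because Section 5.1 reserves a named drug for that drug alone, neither line can be read loosely as referring to the combination.

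Sites will use these tables patient by patient. A site reading only Table 10 for a DLT that has come back after a reduction is told to end the drug not under suspicion and is told nothing about the drug that is. A site reading only Table 9 for a Grade 2 cardiac event that it attributes to sonidegib is told to halve buparlisib and is told nothing about sonidegib. The stake is safe and consistent dosing, not the estimate of response rate.

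**Working it through.** The plan gives no figure to reproduce here. The check is to set each line against its table's scope, look for text that corrects it, and count the situations left over.

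**Line 1: Table 10 footnotes**

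1. The table's scope is buparlisib, but both footnotes name sonidegib. The recurrence sentence is identical to the one under Table 9, which suggests that it was carried over.
2. Text that limits the effect: Section 4.1 stops both drugs at a DLT, and a recurrence is itself a DLT. Section 4.1.1 takes a patient needing more than one reduction off the study. Section 4.1 has no recurrence rule of its own.
3. Where the footnote could still matter. Assume that DLTs are Grade 3 or 4 events (the reviewed text gives no DLT definition for this study). Outside the three overlap classes, Table 10 has 9 event classes: glucose, LVEF, QTc (referred to Table 9), other cardiac, mood, rash, fatigue, pneumonitis (referred to Table 14) and other adverse events. The nausea/vomiting note is not counted. 9 × 2 grades = 18 cells.
   - Outright discontinuation: LVEF 2 + QTc 1 + other cardiac 2 + mood 2 + rash 2 + fatigue 2 + pneumonitis 1 + other 2 = 14.
   - Restart or continuation possible: 18 − 14 = 4 (glucose Grades 3 and 4 if improved, QTc Grade 3, pneumonitis Grade 3).
   - QTc has its own second-occurrence rule in Table 9, and glucose has recurrence rules in Table 10 and Section 4.1.2.2.1. That leaves Grade 3 pneumonitis, restarted at half dose under Table 14, as the main listed case.
4. In the three overlap classes the both-drug rule works by grade. On recurrence, the footnotes of both tables name only sonidegib.
5. The 21-day footnote has no separate effect: Sections 4.1, 4.1.1 and 4.2.1 already cover buparlisib delays.

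**Line 2: Table 9, Other Cardiac Events, Grade 2**

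1. Table 9 has 12 rows that call for a 50% reduction: neutropenia 3/4, thrombocytopenia 3/4, febrile neutropenia 3, creatinine 1.5–3 × ULN, creatinine 3, bilirubin 1.5–3 × ULN, bilirubin 3, AST/ALT 3, AST/ALT 4, QTc 3, other cardiac 2 and other adverse events 2. Only the other-cardiac row names an individual drug, and it names buparlisib. (The muscle rows name sonidegib but give no percentage, so they fall outside this count.)
2. The both-drug rule lists hematologic, renal and hepatic toxicities, so it does not reach this row. Where one table is meant to serve both drugs for a cardiac event, the plan says so: for QTc, Table 10 refers to Table 9. There is no such reference here.
3. Two cases by causality:
   - *Unclear or joint.* Section 4.1 allows both drugs to be adjusted, and Section 4.3.3 by default attributes adverse events to the combination. Sonidegib can therefore already be reduced.
   - *Clearly sonidegib.* The causal-drug rule leads to Table 9, which changes the other drug. Buparlisib goes from 80 mg to 0.5 × 80 = 40 mg; sonidegib stays at 200 mg.

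**The case against.** The strongest reply on line 1 is that the footnote omits something but permits nothing. A reader might infer that Table 10 lets buparlisib continue after a recurrent DLT. It does not say that, and Sections 4.1 and 4.1.1 point the other way. No patient can be shown to stay on buparlisib because of this sentence. That stands, and it limits the weight of line 1. It does not make the footnote right: the buparlisib table still gives no recurrence instruction for buparlisib.

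On line 2, a reader might infer that nothing in the plan lets the investigator adjust sonidegib after a Grade 2 cardiac event. That goes too far. The unclear-causality rule and the default attribution in Section 4.3.3 allow it, dose changes are to be discussed with the sponsor, and Table 9 permits case-by-case departure. The gap is confined to events clearly attributed to sonidegib.

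Line 2 may also be deliberate. Table 10 reduces or stops buparlisib for falling LVEF, Section 4.1.2.3 treats cardiac events as a buparlisib matter, and Sections 1.4.2 and 1.4.7.2.1 report little cardiac signal with sonidegib. The documents do not settle this. Even if it is intended, a row governing suspected sonidegib events needs a sonidegib instruction.

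**Conclusion.** The point holds as a drafting error in operative dosing text that is worth correcting. Line 1 leaves the buparlisib table without a recurrence instruction for its own drug. Neighbouring rules contain the harm, and the main listed case is recurrent Grade 3 pneumonitis, if that counts as a DLT. Line 2 is one row at one grade and misdirects the action only when the event is clearly attributed to sonidegib.

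Both situations are probably rare; the documents give no rate for either. No sample size, error rate or planned estimate is affected. The conclusion rests on reading named drugs as Section 5.1 says they should be read. The case count for line 1 also rests on the assumption that DLTs are Grade 3 or 4 events.

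**What to change.** 1. **Table 10 footnotes.** Name buparlisib in place of sonidegib in the recurrence sentence, and change the 21-day footnote to refer to toxicity related to buparlisib. Do not add blanket study discontinuation here: Section 4.1.2.2.1 allows up to two dose reductions in hyperglycemia management, which such a rule would contradict.
2. **Table 9, Other Cardiac Events, Grade 2.** Direct the 50% reduction at sonidegib, or at both drugs if the sponsor also intends a buparlisib reduction. The sponsor should confirm which.

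The cost is the wording of three table lines, with no change to sample size or analysis. How a 100 mg sonidegib dose (0.5 × 200 mg) is to be given when only 200-mg units are supplied is a separate question. It already arises for the other 11 half-dose rows of Table 9 and need not hold up this correction.

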4.1.1 Monitoring of buparlisib suspected toxicities

Patients whose treatment is interrupted or permanently discontinued due to an adverse event or clinically significant laboratory value, must be followed at least once a week for 4 weeks, and subsequently at 4-week intervals, until resolution or stabilization of the event, whichever comes first. If a patient requires a dose delay of > 21 days from the intended day of the next scheduled dose, then the patient should be discontinued from the study. If the patient requires more than 1 dose reductions, the patient should be discontinued from the study (ie, patients cannot be treated below a 50% dose reduction). All patients must be followed for adverse events and serious adverse events for 28 days following the last dose of buparlisib. All SAEs must be reported to Novartis as detailed in Section 4.3.4.2.

4.1.2 Known Undesirable Side Effects of buparlisib

4.1.2.1 Neuropsychiatric events

In an ongoing phase 1a study of buparlisib in patients with solid tumors (CBKM120X2101), neuro-psychiatric adverse events, including reversible and generally mild to moderate mood alterations, described as anxiety, agitation with crying episodes and depression have been reported in patients treated with buparlisib. In this study, three out of five patients with moderate to severe mood alterations had a history of depression and/or anxiety. All patients with a documented medical history of depression/anxiety also developed mood alterations while treated with buparlisib at the 100 mg dose level and thus reflecting a potential risk group of patients.

In order to lower the risk of experiencing significant mood alterations within the proposed study, cancer patients with an active or history of major depressive episode, bipolar disorder, obsessive-compulsive disorder, schizophrenia, a history of suicide attempt or ideation, or homicide/homicidal ideation as judged by the investigator and/or based on recent psychiatric assessment will not qualify for study participation. Patients with corresponding symptoms CTCAE Grade ≥ 2 should immediately be examined by a psychiatrist and closely followed medically. Medical treatment with mood stabilizers (2^{nd} generation antipsychotics) such as olanzapine and quetiapine may be applied as per investigator's discretion and following consultation of a psychiatrist.

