Mild mood alteration (or Grade 2 anxiety if present at baseline)	Note : If question 9 (suicidal ideation) on the PHQ-9 has a positive response, or worsens in severity, the patient should be referred for psychiatric consult regardless of the total questionnaire score
Grade 2 Moderate mood alteration (for	Institute appropriate co-medication under the guidance of the psychiatrist. Maintain dose level.
Anxiety only, if worsened from baseline) and if there is no concurrent medical condition that accounts for an acute increase the PHQ score.	If the condition does not resolve to ≤ Grade 1 within 14 days despite medical treatment; then implement 50% dose reduction (continue to co-medicate) Note: If question 9 (suicidal ideation) on the PHQ-9 has a positive response, or worsens in severity, the patient should be referred for psychiatric consult regardless of the total questionnaire score
Grade 3	Discontinue study medication
Severe agitation; hospitalization not indicated	Note : If question 9 on the PHQ-9 has a positive response, or worsens in severity, the patient should be referred for psychiatric consult regardless of the total questionnaire score
Grade 4	Discontinue study medication. Consider hospitalization
Life-threatening consequences; urgent	if appropriate
intervention indicated	Note: If question 9 on the PHQ-9 has a positive response, or worsens in severity, the patient should be referred for psychiatric consult regardless of the total questionnaire score

Table 10. Recommended dose modifications and dose delays for suspected buparlisib treatment-related toxicities	
Worst toxicity	During a cycle of therapy
CTCAE grade* (value)	
Rash	
Grade 1 Macules /papules covering <10% BSA with or without symptoms (e.g. pruritus, burning)	Maintain dose level. Consider to initiate appropriate skin toxicity therapy (such as antihistamines, topical corticosteroids)

Grade 2 Macules/papules covering 10-30% BSA with or without symptoms; limiting instrumental ADLs	Reduce study drug dose to 50% of prior dose. Initiate/intensify appropriate skin toxicity therapy (such as antihistamines, topical corticosteroids)
Grade 3 Macules/papules covering >30% BSA with or without associated symptoms, limiting self-care ADLs	Discontinue study drug According to the investigators discretion, a paired skin biopsy could be obtained (from both an affected and an unaffected skin area for local histopathology assessment) if clinical appropriate

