4.2.3 Concomitant therapy

All medications (excluding prior chemotherapy and biologic, immunologic or radiation therapy) taken within 4 weeks prior to the administration of buparlisib/sonidegib and all concomitant therapy administration during the study with reasons for therapy should be recorded. All prior chemotherapy; biologic, immunologic or radiation therapy; and surgery within 4 weeks prior to the administration of study drug, will be recorded.

Patients on chronic medications that can be given concomitantly with buparlisib/ sonidegib should be maintained on the same dose and dose schedule throughout the study period, as medically feasible. The investigator should instruct the patient to notify the study site about any new medications he/she takes after the start of the study drug. All medications (other than study drug) and significant non-drug therapies (including herbal medicines, physical therapy and blood transfusions) administered after the patient starts treatment with study drug, and any changes in dosing should be recorded.

In general, the use of any concomitant medication/therapies deemed necessary for the care of the patient is permitted with the following exceptions described below in Section

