4.2.3.1 Drugs that are prohibited

- ♦♦ Other investigational therapies must not be used while the patient is on the study.
- ◆◆ Anticancer therapy (chemotherapy, biologic or radiation therapy, and surgery) other than the study treatments must not be given to patients while the patient is on the study. If such agents are required for a patient then the patient must be discontinued from the study.
- ♦ In vitro metabolism studies suggest that oxidative metabolism of buparlisib is predominantly mediated by CYP3A4 (fm>0.9), with only minor contributions of CYP1A1. As buparlisib is a sensitive CYP3A4 substrate, co-administration of buparlisib with strong and moderate CYP3A4 inhibitors and CYP3A4 inducers is prohibited. Refer to Table 15 for a list of prohibited drugs. Please note this list may not be comprehensive.
- Based on in vitro studies, co-administration of buparlisib with CYP3A4 inducers is predicted to decrease the systemic exposure to buparlisib, thereby increasing the risk of exposing the patient to subtherapeutic drug levels. Refer to Table 15 for a list of prohibited CYP3A inducers. Please note that this list may not be comprehensive. Therapeutic doses of warfarin sodium (Coumadin®) or any other coumadin-derivative anticoagulants are not permitted.
- •• If a patient requires the concomitant use of any medication included in Table 16 entitled "List of Prohibited QT prolonging drugs" (ie, drugs that are generally accepted by the Qtdrugs.org Advisory Board of the Arizona CERT to have a risk of causing Torsades des de Pointes), study treatment administration must be interrupted as long as the patient requires therapy with the QT prolonging agent.
- ♦♦ Herbal preparations/medications are not allowed throughout the study. These herbal medications include, but are not limited to St. John's wort, Kava, ephedra (ma huang), ginko biloba, dehydroepiandrosterone (DHEA), yohimbe, saw palmetto, ginsing. Patients should stop using these herbal medications 7 days prior to first dose of study drug.

◆◆ Hormonal contraceptives may be affected by cytochrome P450 interactions, and are therefore not considered effective in this study.

Table 15. List of prohibited CYP3A Inhibitors and Inducers

СҮРЗА	Inhibitors	СҮРЗ	3A Inducers
Strong	Moderate	Strong	Moderate

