clarithromycin conivaptan grapefruit juice Indinavir itraconazole ketoconazole Lopinavir Mibefradil nefazodone Nelfinavir posaconazole Ritonavir Saquinavir	aprepitant atazanavir cimetidine ciprofloxacin darunavir diltiazem erythromycin fluconazole tofisopam verapamil amprenavir fosamprenavir elvitegravir tipranavir	avasimibe carbamazepine Phenobarbital (barbiturate) phenytoin rifabutin rifampin St John's Wort	bosentan efavirenz etravirine modafenil nafcillin ritonavir talviraline tipranavir
telithromycin troleandomycin voriconazole			

This database of CYP inhibitors was compiled from the Indiana University School of Medicine's "Clinically Relevant" Table and from the University of Washington's Drug Interaction Database based on *in vitro* studies. Strong inhibitors are predicted to increase buparlisib AUC > 5-fold, and moderate inhibitors are predicted to increase buparlisib AUC ≥ 2-fold but < 5-fold.

This database of CYP inducers was compiled from the FDA's "Guidance for Industry, Drug Interaction Studies;" from the Indiana University School of Medicine's "Clinically Relevant" Table; and from (Pursche *et al.* 2008).

All QT-prolonging drugs listed in Table 4-8 are prohibited for all patients from screening through permanent discontinuation of study treatment. Table 16 below lists drugs with a known risk for Torsades de Pointes (TdP) as well as sensitive CYP3A substrates (with narrow TI) with a possible or conditional risk for TdP.

Table 16. List of prohibited QT-prolonging drugs

Drug	QT risk(*)	Comment
Amiodarone	Known risk for TdP	Females > Males, TdP risk regarded as low
Arsenic trioxide	Known risk for TdP	
Astemizole	Known risk for TdP	No Longer available in U.S.
Bepridil	Known risk for TdP	Females>Males
Chloroquine	Known risk for TdP	
Chlorpromazine	Known risk for TdP	
Cisapride	Known risk for TdP	Restricted availability; Females > Males.
Disopyramide	Known risk for TdP	Females > Males
Dofetilide	Known risk for TdP	
Domperidone	Known risk for TdP	Not available in the U.S.
Droperidol	Known risk for TdP	
Halofantrine	Known risk for TdP	Females>Males
Haloperidol	Known risk for TdP	When given intravenously or at higher-than- recommended doses, risk of sudden death, QT prolongation and torsades increases.
Ibutilide	Known risk for TdP	Females>Males
Levomethadyl	Known risk for TdP	
Mesoridazine	Known risk for TdP	
Methadone	Known risk for TdP	Females > Males
Pentamidine	Known risk for TdP	Females > Males
Pimozide	Known risk for TdP	Females > Males

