Probucol	Known risk for TdP	No longer available in U.S.
Procainamide	Known risk for TdP	
Quetiapine	Possible risk for TdP	Prohibited as this drug is a sensitive 3A4 substrate
Quinidine	Known risk for TdP	Females > Males
Sotalol	Known risk for TdP	Females > Males
Sparfloxacin	Known risk for TdP	
Tacrolimus	Possible risk for TdP	Prohibited as this drug is a sensitive 3A4 sibstrate with narrow TI

Terfenadine	Known risk for TdP	No longer available in U.S.
Thioridazine	Known risk for TdP	
Drug	QT risk(*)	Comment

^(*) Classification according to the Qtdrugs.org Advisory Board of the Arizona CERT Sensitive substrates: Drugs whose plasma AUC values have been shown to increase 5fold or higher when co-administered with a potent inhibitor of the respective enzyme.

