5.1 Investigational treatment

For this study, the terms "investigational drug", "study drug" or "study treatment" refers to the combination of Sonidegib and buparlisib. If an individual drug is to be referenced the individual name will be present.

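### Section 4.1.2.1 suggests quetiapine for mood symptoms but Table 16 prohibits it; at Grade 2, where Table 10 keeps the patient on study drug, the instructions conflict

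*Combined protocol and SAP*

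**What the plan says.** Five places in the combined protocol and SAP bear on this.

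- **Section 4.1.2.1** sends patients with mood symptoms of CTCAE Grade 2 or higher to a psychiatrist. It then gives examples of medication: "olanzapine and quetiapine may be applied as per investigator's discretion".
- **Table 10, mood alteration, Grade 2** (section 4.1): "Institute appropriate co-medication under the guidance of the psychiatrist. Maintain dose level". If the event has not resolved to Grade 1 or lower within 14 days: "then implement 50% dose reduction (continue to co-medicate"). At Grades 3 and 4 the same table discontinues study medication.
- **Table 16** (section 4.2.3.1) lists quetiapine as a possible Torsades risk, with the comment "Prohibited as this drug is a sensitive 3A4 substrate". The sentence introducing the table sets the scope: "All QT-prolonging drugs listed in Table 4-8 are prohibited for all patients from screening through permanent discontinuation of study treatment". No Table 4-8 exists in this protocol. The table that follows that sentence is Table 16, and exclusion criterion 14 also cites Table 16 as the prohibited list.
- **Section 4.2.3.1** also says what happens if a patient needs a Table 16 drug: "study treatment administration must be interrupted as long as the patient requires therapy with the QT prolonging agent". Section 5.1 states that study treatment "refers to the combination of Sonidegib and buparlisib".
- **Section 4.2.3** sets the general rule. Concomitant medication that the patient needs "is permitted with the following exceptions described below in Section"; the section number is missing from the sentence, but the prohibited list in 4.2.3.1 comes next.

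**The concern.** Two safety instructions in one protocol disagree about a named drug. An investigator who turns to the neuropsychiatric section, which is the natural place to look when a patient on buparlisib develops depression or anxiety, finds quetiapine as one of only two drugs named. Nothing there refers to the prohibited list.

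A reader who does check can still be misled. Section 4.2.3.2 allows drugs with a possible or conditional Torsades risk at the investigator's discretion and cites Table 16 as the list of drugs to use with caution. The caution list is actually Table 18. Quetiapine's row in Table 16 carries the possible-risk label, so the wrong table number makes it look permitted, although the next line of 4.2.3.2 calls Table 16 the prohibited list.

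The outcome is one of two departures from the protocol. Either a prohibited drug is given alongside study treatment, or both study drugs are interrupted where Table 10 wants the dose kept or halved. The second has its own cost, because under sections 4.1.1 and 4.2.1 a delay of more than 21 days leads to discontinuation. Section 4.1 makes an exception for toxicity-related delays in patients with clinical benefit. For the first, Table 19 and section 4.3.5.6 schedule no ECG after screening except as clinically indicated.

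**Working it through.** There is no planned figure to reproduce. The check sets the instructions side by side for a patient given quetiapine.

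| Mood event | Table 10 or 4.1.2.3.3 | 4.2.3.1 and Table 16 while quetiapine is needed | Compatible? |
|---|---|---|---|
| Grade 2, first 14 days | Co-medicate, dose unchanged | Drug prohibited; both study drugs interrupted | No |
| Grade 2, unresolved after 14 days | Half dose, co-medication continues | Drug prohibited; both study drugs interrupted | No |
| Grade 3 or 4 | Study medication discontinued | Prohibition ends at permanent discontinuation | Yes, once study treatment has permanently stopped |
| PHQ-9 question 9 positive | 4.1.2.3.3: buparlisib omitted pending psychiatric advice | Both study drugs interrupted | Dosing conflict reduced: buparlisib is already held |

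With olanzapine in place of quetiapine, the first two rows become compatible. The following counts support that.

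1. Table 16 as it appears in the text available to me has 28 drugs. Quetiapine is one of them and olanzapine is not.
2. Table 18 has 52 drugs. Neither quetiapine nor olanzapine is among them.
3. No drug appears in both tables, so Table 18 does not soften the Table 16 entry.

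The grade at issue is defined in Table 13: Grade 2 is a PHQ-9 score of 10 to 19 or a GAD-7 score of 10 to 14. Section 4.1.2.3.3 leaves the final grade to clinical judgement.

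Table 7 gives some idea of how common mood events are on buparlisib at 100 mg/day:

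- Patients: 55 + 9 + 50 + 12 + 6 = 132
- Any grade: 11 + 4 + 6 + 7 + 0 = 28
- Grade 3-4: 2 + 0 + 0 + 2 + 0 = 4
- Grade 1-2 by subtraction: 28 − 4 = 24, and 24/132 = 18.2%

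The subtraction assumes that each patient is counted once, at the worst grade. The result is a ceiling on Grade 2 in those studies and not an estimate for this trial. Grade 2 is not reported separately, this trial uses 80 mg, and the share of patients who would receive quetiapine is not given anywhere.

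**The case against.** The strongest reply is that nothing forces the conflict. Section 4.1.2.1 is permissive, its two drugs are examples, and the choice is made with a psychiatrist. Table 10 asks for suitable co-medication without naming a drug. Section 4.2.3 makes the prohibited list an exception to whatever else is allowed. An investigator who reads everything together uses olanzapine and breaks no rule. This is correct as far as it goes: the instructions clash only if quetiapine is chosen. But 4.1.2.1 itself proposes that choice.

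A second reply is that interruption is less clearly required than it looks. Section 4.2.3.1 describes Table 16 drugs as those generally accepted to carry a Torsades risk, whereas quetiapine is labelled a possible risk and is barred on CYP3A4 grounds. Section 4.2.3.2 lets possible-risk drugs be given at discretion. This adds ambiguity but does not permit the drug. Quetiapine is prohibited by name, is absent from Table 18, and 4.2.3.2 itself refers to Table 16 as the prohibited list.

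A third reply is that the Table 16 row might be the mistake. The text before the table says it includes sensitive CYP3A substrates with a narrow therapeutic index; tacrolimus's row mentions narrow index and quetiapine's does not. The documents do not settle which entry the authors would keep. Moving quetiapine to Table 18 would also remove the conflict, but that relaxes a safety restriction, which needs a pharmacological justification that the protocol does not offer.

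A fourth reply is that deleting quetiapine loses a valid option at Grades 3 and 4, after study drug has stopped. It does not: removing an example from an illustrative list prohibits nothing once study treatment has permanently ended.

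Finally, the harm is small. Section 4.2.3.2 calls buparlisib a weak, reversible CYP3A4/5 inhibitor and says the data cannot confirm that such interactions occur in patients. That stands, and it limits the weight of the point.

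**Conclusion.** The inconsistency is real. At Grade 2 with quetiapine chosen, the suggestion in 4.1.2.1, the dosing rule in Table 10, and the prohibition and interruption rule in 4.2.3.1 cannot all be followed. The conclusion takes the 'Table 4-8' reference to mean Table 16 and gives the listing of quetiapine by name precedence over the general discretion in 4.2.3.2.

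Its reach is one optional drug at one grade. Expected harm is limited, because a psychiatrist is involved, olanzapine is available and the interaction is unconfirmed. The number of patients affected cannot be estimated. The analysis of overall response rate is unaffected. It should still be corrected, because mood alteration is a known buparlisib effect with its own management pathway here, and the text that investigators will consult proposes a drug the protocol bans.

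**What to change.** In section 4.1.2.1, delete quetiapine, keep olanzapine, and add a reference to Table 16 for prohibited drugs. Table 10 then needs no change.

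In the same amendment, correct two table numbers: in 4.2.3.2, cite Table 18 instead of Table 16 as the list of QT-prolonging drugs to use with caution; in 4.2.3.1, replace the reference to Table 4-8 with Table 16.

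The cost is wording only: one drug name removed, one cross-reference added and two numbers corrected. Design, sample size and analysis do not change.
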